#### 2. BACKGROUND

The surgical approach for cervical cancer staging has changed from conventional laparotomy to a more minimally invasive technique with proven advantages in terms of less perioperative morbidity. Robotic assisted laparoscopic radical hysterectomy with pelvic lymph node dissection has emerged as the approach of choice for an increasing number gyne-oncologists worldwide. Previous data from the department of Obstetrics and Gynecology in Lund, Sweden, shows that robot assisted surgery feasible for 95% of unselected cervical cancer patients selected for primary surgery. In cervical cancer, nodal involvement is a strong prognostic factor and also determines

adjuvant treatment and a pelvic lymphadenecomy is recommended for cervical cancer stages 1a2 and higher stages where primary surgery is recommended. A pelvic lymphadenectomy is associated with an increased risk for lymphatic complications such as lymphedema, lymphocysts and in rare cases lymphatic ascites.

The concept of identifying nodal metastases by detection of sentinel lymph nodes as a marker of nodal metastatic disease or not therefore is appealing. However, during later years many studies have been published, most of the retrospective, using a variety of tracers and with little or no information on used surgical algorithm, used definition of SLN and without reference to lymphatic anatomy. Moreover, technical success rate varies. A high technical success rate is cruzial to avoid the need for a full hemipelvic or pathwaywize LND in case of failure. In pilot studies from Lund University we have shown that reinjection of tracer (ICG) increases the technical success rates both defined per hemipelvis and pathwaywize, defined by detection of at least one SLN per hemipelvis to around 95%. By the use of Indocyanine green, a fluorescent tracer, we have also previously demonstrated two bilateral separate pelvic pathways, the upper paracervical pathway (UPP) running along the upper lymphovascular parametrium usually to external iliac and/ or obturator nodes and the further lateral to the common iliac artery to paraaortic nodes and the lower paracervical pathway (LPP) running via the sacrouterine ligament to nodes medial of the internal iliac artery and/ or presacral nodes then further medial to the common iliac artery to paraaortic nodes. Hence there are two bilateral pelvic pathways draining further to the paraaortic region below as well as above the inferior mesenteric artery.

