#### 8.0 EVALUATION CRITERIA

-Technical success rates, sensitivity and false negative rates with ICG and Tc99 nanocolloid will be compared per patient, per hemipelvis and per pathway, UPP and LPP.

- All patients who are injected with tracer and not converted to open surgery before detection and removal of SLN's will be included for evaluation of technical success rate (described per patient, per hemipelvis and per separate pathway) after first and in case of non-dispay of any of the LPP and UPP after reinjection of ICG as described.

- Patients with at least one SLN type1-2 identified will be included for determining the sensitivity and the negative predictive value for the SLN ICG concept. In addition the overall SLN concept, including SLN macro will be evaluated as of above.

- All patients included, regardless of conversion to open surgery and mapping of ICG (or the combination of ICG and Tc99 nanocolloid) will be included in the evaluation of feasibility and safety.

- Intraoperative adverse associated with the detection and removal of SLN will be evaluated and reported separately on all patients who have at least one SLN removed regardless of type, i.e all patients in whom SLN were removed separately.

- Postoperative complications until 30 days after surgery will be reported.

-The incidence of lymphatic complications defined by the questionnaire will be evaluated

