### Sentinel node in cervical cancer Version 1.2 180914 11. STATISTICAL CONSIDERATIONS

This study is designed to evaluate the application of the sentinel node (SLN) technique in determining the pelvic lymph node (LN) status in patients with early stage cervical cancer ( stage 1a2 to 2a1) planned for primary surgery with either a radical hysterectomy or radical abdominal trachelectomy.

The main statistical endpoint will be sensitivity and false negative rates /negative predictive value calculated per patient. The sensitivity is the proportion of patients who test as SLN (+) among the patients who have LN metastases (LN+). The patients will, according to the Swedish national guidelines for early stage cancer undergo a full pelvic lymphadenectomy, however with separate removal of SLN as defined above, hence serve as their own controls. As lymph node status (lymph node metastases or no lymph node metastases) is a definite parameter (false positive result can by definition not occur) specificity and positive predictive values will not be reported in this study.

The time for accrual may have to be revised revised after inclusion of additional participating centers.

We used the Fleming two stage design for evaluation of study termination for evaluating if the technique is not working well, as expected or better (Fleming, 1982).

The null hypothesis that the sensitivity is 85% will be tested against one-sided alternative. The study is terminated after stage one if it is unlikely that the sensitivity is  $\geq$  95% or if sensitivity is significantly higher than 85%. In the first stage, 34 LN+ patients will be accrued. If there are 30 or fewer responses in these 34 patients, the study will be stopped for futility. If there are at least 33 responses in 33 patients, the study will be stopped and the null hypothesis rejected. Otherwise, 28 additional patients will be accrued for a total of 62 node positive patients. The null hypothesis will be rejected if 58 or more responses are observed in 62 patients. This design yields a type I error rate of 0.05 and power of 0.8 when the true sensitivity is 92.5

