For the first stage we estimated a total of 226 patients to be included taking into consideration a 95% bilateral SLN detection rate, and an estimated 15% rate of node positivity including an increase in node positivity rates due to ultrasectioning and immunohistochemistry. For the second stage, another 187 patients have to be included. As the number of node positive patients will be reported continuously to the study coordinator this will be decisive of the number of patients that has to be included for each stage.

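### Sections 8 and 11 define the population for the main sensitivity endpoint differently, and neither says which node-positive patients or which SLN concept are judged against the 34- and 62-patient boundaries

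*Combined protocol and SAP*

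**What the plan says.** Section 11 makes per-patient sensitivity, with the false negative rate and negative predictive value, the main statistical endpoint. It defines it thus: "The sensitivity is the proportion of patients who test as SLN (+) among the patients who have LN metastases (LN" (the abbreviation is LN+). No mapping condition is attached. The test is stated on the same footing: "The null hypothesis that the sensitivity is 85% will be tested against one-sided alternative", and "In the first stage, 34 LN+ patients will be accrued". The total after stage 2 is 62 node-positive patients.

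Section 8 sets a different inclusion rule: "Patients with at least one SLN type1-2 identified will be included for determining the sensitivity". It applies this to the concept based on ICG, then says that an overall concept including SLN macro (macroscopically suspect nodes, whatever their tracer uptake) will also be evaluated. Section 6 separately removes patients converted to open surgery before SLN removal from the sensitivity calculation.

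A 95% bilateral detection rate appears only where patient numbers are discussed. Section 9 says it would add about 15 patients and then mentions extra positives from ultrasectioning as an offset. Section 11 says that the stage 1 total was reached "taking into consideration a 95% bilateral SLN detection rate". Section 9 starts the interim analysis at 36 node-positive patients, against 34 in section 11.

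**The concern.** Take a node-positive patient in whom no type 1 or type 2 SLN was found. Under section 11 she is one of the 34 and counts as a miss. Under section 8 she is not in the sensitivity analysis at all. If her only positive node was macroscopically suspect and removed as SLN macro, she may count as a success under the overall concept. One patient can therefore be a failure, an exclusion or a success, depending on the section followed.

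The boundaries leave no room for this. Stage 1 separates stopping for futility from rejecting the null by three patients (30 against 33), and the final test turns on 58 against 57. Section 10.1.4 has potential false negatives reported continuously to the study coordinator, so a denominator left open now would be settled with the outcomes known.

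**Working it through.** **Inputs.** From section 11: null sensitivity 85%, one-sided; stage 1 size 34 with futility at 30 or fewer; 28 more patients; final rejection at 58 or more of 62. The stage 1 efficacy bound is printed as 33 responses in 33 patients. I read it as 33 of 34, because that reading comes closest to the stated type I error: 0.049, against 0.034 for 34 of 34 and 0.027 for a stage 1 of 33 patients with the total kept at 62. The share *u* of LN+ patients without a type 1-2 SLN is not in the documents. I assume 1%, 2% and 5%.

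**The plan's own figures.** With X1 successes in stage 1 and X2 in the next 28:

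P(reject) = P(X1 ≥ 33) + P(X1 = 31)·P(X2 ≥ 27) + P(X1 = 32)·P(X2 ≥ 26)

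- At 85%: 0.0279 + 0.1310 × 0.0627 + 0.0696 × 0.1871 = 0.049.
- At 95%: 0.4877 + 0.1525 × 0.5883 + 0.2717 × 0.8373 = 0.805.
- At 92.5%: 0.517.

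Section 11 says: "This design yields a type I error rate of 0.05 and power of 0.8 when the true sensitivity is 92.5". The type I error reproduces. The power reproduces at 95%, the value section 11 uses for its stage 1 stop, and not at the printed 92.5%. That is a separate defect. I use 95% below because it is where the rule delivers its 0.80.

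**(a) Section 11 followed: unmapped LN+ patients count as misses.** With 95% sensitivity among mapped patients, effective sensitivity is 0.95 × (1 − u).

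| u (assumed) | Effective sensitivity | Power | P(stage 1 futility stop) |
|---|---|---|---|
| 0 | 95.0% | 0.805 | 0.088 |
| 1% | 94.05% | 0.700 | 0.141 |
| 2% | 93.1% | 0.587 | 0.205 |
| 5% | 90.25% | 0.291 | 0.426 |

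**(b) Section 8 followed: unmapped LN+ patients are excluded, and 34 and 62 mapped patients are analysed.** If sensitivity in all LN+ patients is exactly 85%, sensitivity among the mapped is 0.85/(1 − u). At u = 5% this is 0.85/0.95 = 89.5%, and the rule rejects with probability 0.231. This is not a type I error for the section 8 quantity. It shows that the two sections test different hypotheses.

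**(c) Both followed: accrue 34 LN+ patients, then drop one as unmapped, bounds unchanged.** Stage 1 has 33 patients and the total is 61. At 95%: P(33 of 33) + P(31 of 33)·P(X2 ≥ 27) + P(32 of 33)·P(X2 ≥ 26) = 0.1840 + 0.2692 × 0.5883 + 0.3196 × 0.8373 = 0.610. If stage 2 is extended by one patient to restore 62, power is 0.708.

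**The bilateral allowance.** 34/0.15 = 226.7, 28/0.15 = 186.7 and 62/0.15 = 413.3. The stated 226, 187 and 413 are therefore LN+ counts divided by prevalence, with no 95% factor. With it, stage 1 needs 34/(0.15 × 0.95) = 239 patients and the whole trial 62/(0.15 × 0.95) = 436. Conversely, 226 × 0.15 × 0.95 = 32.2, short of 34.

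**The case against.** The best defence is that section 8 merely describes the evaluable subset of the section 11 definition, as section 6 does for early conversions. That is a fair reading, and it makes this an unresolved ambiguity more than a flat contradiction. It does not remove the problem: section 11 still counts 34 and 62 in LN+ patients, and dropping some of them afterwards gives case (c). Nor does it settle whether SLN macro counts.

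It is also fair that the size depends on *u*, which the plan does not give. If every LN+ patient has at least one type 1-2 SLN, the two sets coincide and nothing is lost.

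Two stronger readings are tempting, and the documents do not carry them.

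- A reader might infer a third denominator, bilaterally mapped patients, that the sample size already assumes. No section defines sensitivity in that set. The interim trigger of 36 fits it (34/0.95 = 35.8), but that is inference, and the totals of 226 and 413 contain no such allowance.
- A reader might infer that counting unilaterally mapped patients penalises mapping failure twice and destroys the power. Section 2 wants high technical success "to avoid the need for a full hemipelvic or pathwaywize LND in case of failure", so in practice an unmapped side would be dissected. But technical success and per-patient sensitivity are separate endpoints, and counting disease on the unmapped side as a miss is a legitimate, conservative convention. The power loss would need 95% to be sensitivity conditional on bilateral mapping, which section 11 does not say. It would also need an unsourced share with disease only on the unmapped side: at 5% unilateral mapping, power is 0.53 if that share is one half but 0.75 if it is one tenth. Section 2 also speaks of pathways, so the same logic would exclude patients lacking one pathway.

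**Conclusion.** The point holds as an unfixed primary analysis set. Sections 8 and 11 differ on which LN+ patients enter the main endpoint, and no section says which SLN concept meets the boundaries. The choice can decide the trial: against a power of 0.805 at 95%, one dropped patient in stage 1 gives 0.61, and counting unmapped patients as misses gives 0.70 to 0.29 for assumed shares of 1% to 5%. In the other direction, excluding 5% lets the rule reject with probability 0.23 when sensitivity in all LN+ patients is only 85%.

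These figures rest on reading the stage 1 efficacy bound as 33 of 34, on 95% as the alternative, and on the assumed *u*. They do not show that the design fails in the set section 8 describes: if 34 and then 62 patients are counted within that set, the exact type I error of 0.049 and power of 0.805 at 95% apply to it. Because the rule drives both stopping and rejection, the plan should settle this before the interim analysis.

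**What to change.** In section 11, name one primary set and one SLN concept (ICG-defined, or overall with SLN macro) for the boundary test, and repeat both in section 8. One workable choice is the set section 8 already states: LN+ patients with at least one type 1-2 SLN. Count the 34 and the 62 in that set, and trigger the interim analysis when its 34th member is confirmed, in place of the separate figure of 36. State how the section 6 conversions are handled. Report sensitivity in all LN+ patients and in bilaterally mapped patients as prespecified supportive estimates without a boundary.

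The cost is mostly wording. With the section 8 set, the tested sensitivity applies only to mapped patients, so it must be read beside the technical success rate. Accrual may run a little longer. At 15% prevalence and an assumed *u* of 2%, 62/(0.15 × 0.98) = 422 patients against 413; at 5%, 436. At section 9's pace of about 5 patients a month (226 in 45 months), that is roughly 2 to 5 months.

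Making bilaterally mapped patients the primary set is possible but is a trade-off, not a correction: it needs about 239 and 436 patients at the plan's own rates and narrows the claim further.

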#### **1. OBJECTIVES**

To estimate ICG and Radiocolloid alone and in combination to estimate any advantage of the combination of both tracers in terms of technical success rates/ bilateral mapping, sensitivity and false negative rates for the detection of pelvic SLN (first 75 patients).

To estimate the sensitivity and negative predictive value of the pelvic sentinel lymph node (SLN) concept for determination of lymph node metastases in patients with early stage cervical cancer planned for robotic surgery using either a combination of ICG and Radiocolloid or in case ICG alone is equal to or superior (in terms of technical success rate, bilateral mapping rates) to the combination the use of ICG as tracer for cervical injection using an anatomically based surgical algorithm and definition of sentinel lymph nodes.

To estimate if reinjection of tracer (ICG) will enhance the technical success / bilateral mapping rates.

To estimate the proportion of cervical cancer patients suitable for the SLN concept in conjunction with robotic surgery

To estimate complications associated with the detection and removal of SLN as such.

To estimate complications associated with ICG as tracer.

To estimate the incidence of lymphatic complications by the use of a validated questionnaire

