#### Sentinel node in cervical cancer Version 1.2 180914 5.0 TREATMENT PLAN

-Intraoperative cervical injection of Tc 99 nanocolloid and ICG (immediately before onset of surgery)

-Intraoperative lymphatic mapping and sentinel node identification with robotic NIR/fluorescence imager and gamma probe will be used for an initial transperitoneal, then retroperitoneal evaluation of display of ICG fluorescence/ radiopositivity. The retroperitoneal dissection with opening of the avascular planes saving the lymphatic vessels will start presacrally then further with the pelvic side walls. The upper lymphovascular parametria will be kept intact by a careful opening of the pararectal and paraveiscal spaces. -An ipsilateral reinjection of ICG will be performed in case of non-display of either of UPP or LPP. If the sentinel node cannot be identified in a particular pathway following a 15-20 minute search, the case should be described as a ICG-negative mapping event for that pathway. A initial scanning of the pelvic side walls and presacral area will be performed - A reinjection of ICG will be performed in case of non-display of the UPP and LPP bilaterally.

-The results of the lymphatic mapping will be marked on the anatomic plan and the specimens and labeling of those will be according to descriptions above.

-The complete SLN algorithm should be adhered to, i.e in case of a ICG negative mapping (for **SLN type 1 and 2, ICG defined**) and / or radio negative mapping any macroscopically metastase suspect nodes should be removed and defined as **SLN macro**. All patients will be subject for at least a full pelvic lymphadenectomy after removal of SLN.

-The upper lymphocascular parametrial tissue (the tissue medial of the obliterated umbilical artery, with the supravesical artery as distal/ventral border, the ureter as dorsal border and including tissue adjacent to the inner side of the broad ligament) will be removed and evaluated the same way as SLN's. This is to investigate the presence of lymph node in the upper parametria, theoretically the most juxtauterine nodes, hence the SLN.

-All SLN and the upper parametrial tissue will be subject for later ultrasectioning and IHC Histopathologic evaluation.

 In case of metastatic SLN the lymphadenectomy will be extended to the level of the inferior mesenteric artery and the hysterectomy aborted in favour of radiochemoptherapy. In case of a planned trachelectomy this will be transformed to

a radical hysterectomy.

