-A Querleu-Morrow type B2 or C2 hysterectomy or robotic radical trachelectomy will be performed as appropriate or aborted in case of metastatic LSN at surgeons discretion and patients' wish.

- Adnexal surgery or transpositioning of the adnexa shall be performed at surgeons discretion and patient' wish.

- Complications will be recorded and subdivided to enable association with parts of the procedure, most importantly, the SLN procedure as such and the lymphadenectomy. The classification described under the adverse events tables will be used.

NOTE: Surgeon skill and adherence to protocol will be verified as described.

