#### 6.0 TREATMENT MODIFICATIONS

In case of no ICG uptake (including reinjection according to protocol) or radiopositivity the overall SLN algorithm should be followed, i.e removal of any macroscopically suspect nodes and as planned a full compartmentwize lymphadenectomy.

In case of conversion to open surgery before identification and removal of SLN's the patients should be included in evaluation of adverse events and feasibility on an intention to treat basis but not included in the calculation of sensitivity and negative predictive values for the sentinel node concept.

In case of metastatic SLN on frozen section, the lymphadenectomy should be extended to the level of the inferior mesenteric artery, a planned trachelectomy converted to a radical hysterectomy and at surgeons discretion and patient wish a planned radical hysterectomy completed or aborted in favour of radiotherapy. Adnexal surgery / transposition of ovaries shall be performed at surgeons' discretion and patient wish.

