#### 9.0 DURATION OF STUDY

The study includes a radical hysterectomy/ radical abdominal trachelectomy with detection of SLN followed by a full pelvic lymphadenectomy along both the UPP and LPP.

The patient may withdraw from the protocol at any time prior to surgery or at any time until retrieval of postoperative data until one year after surgery.

The study is initiated at Lund University hospital with a planned later inclusion of the second investigating center which may motivate a revision of the study protocol related estimated time for enrollment of patients and for accreditation of the second centre and surgeons.

Assuming that the prevalence of pelvic lymph node metastases is 15 % 227 patients will be needed to obtain 34 lymph node positive observations. Given a 95% bilateral detection rate of SLN's approximately 15 patients more will need to be included. On the other hand, ultrasectioning and IHC of SLN's is estimated to increase the proportion of patients with nodal metastases by identifying micro metastases. As there will be a continuous report of node positive patients to the study coordinator an interim analysis will start after 36 node positive patients regardless of the total number of patients included. (see 11, statistical considerations) Accrual will not be suspended during the interim analysis as the intervention is estimated to pose minimal risk to patients and the national treatment protocol, recommending a full lymphadenectomy, will be followed, even in the event of futility.

If the trial continues to stage 2, another 28 node positive patients (total 187 patients) will be required. (see 11, statistical considerations)

Given an estimate that the accrual rate is 2,5 cervical cancer patients per month per center, a total of 45 months will be required to reach 226 cervical cancer patients and a total of an additional 37 months to reach 413 patients.

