# Adverse events related to the sentinel node procedure as such (excluding AE related the study drug, ICG)

All intraoperative events related to the SLN procedure will be reported on the adverse events log.

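### The separate report on SLN-procedure adverse events covers only patients with an SLN removed, so it leaves out injuries during a search that yields no node or is cut short by conversion

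*Combined protocol and SAP*

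**What the plan says.** - **Objective.** Section 1 lists, as an objective in its own right: "To estimate complications associated with the detection and removal of SLN as such". Detection is named alongside removal.
- **Analysis set for that objective.** Section 8.0 says that intraoperative adverse events of SLN detection and removal "will be evaluated and reported separately on all patients who have at least one SLN removed regardless of type". It then glosses the set as the patients whose SLN were taken out as a separate step.
- **Overall safety set.** The bullet just before it in section 8.0 is wider. It puts "All patients included, regardless of conversion to open surgery and mapping of ICG" (or of the combined tracers) into the evaluation of feasibility and safety.
- **Conversions.** For conversion to open surgery before SLN are identified and removed, section 6.0 says "the patients should be included in evaluation of adverse events and feasibility on an intention to treat basis".
- **Recording.** Section 10, on adverse events of the sentinel node procedure as such, says "All intraoperative events related to the SLN procedure will be reported on the adverse events log". It does not require that a node was removed. Table 10.2 is the log for events during sentinel node dissection.
- **Attribution.** Section 5.0 says "Complications will be recorded and subdivided to enable association with parts of the procedure, most importantly, the SLN procedure as such and the lymphadenectomy".

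**The concern.** Looking for an SLN is itself surgery. Sections 4.0 and 5.0 describe opening the presacral, paravesical and pararectal planes, possible reinjection of tracer, and a search of 15 to 20 minutes in a pathway before mapping is declared negative. All of this can come before the first node is taken, so an injury can occur in a patient who never reaches removal.

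Section 8.0 admits a patient to the SLN-specific report only if the procedure reached a particular result. Anyone weighing the technique needs the risk once a search begins, because nobody knows beforehand whether it will yield a node. The clearest difficulty is a search injury that itself causes conversion: the event then removes its own patient from the report meant to count it. What is at stake is one descriptive secondary result, the complication rate of the SLN step.

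**Working it through.** **Step 1: compare the scopes.**
- The objective (section 1) covers detection and removal.
- The log (section 10, Table 10.2) covers all SLN-procedure events.
- The conversion rule (section 6.0) keeps patients converted before removal in the adverse-event evaluation.
- The SLN-specific report (section 8.0) covers only patients with at least one SLN removed.

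The last is narrower than the other three. Section 8.0 also leaves patients converted before SLN detection and removal out of technical success. A patient converted because of a search injury before removal is therefore absent from both SLN-specific outputs, though present in overall safety.

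**Step 2: who is left out.** Only patients with no SLN of any type removed. A patient with failed mapping on one side stays in if the other side gives a node. After negative mapping, section 5.0 says "any macroscopically metastase suspect nodes should be removed and defined as" SLN macro, and these count too. Section 9.0 plans with "Given a 95% bilateral detection rate of SLN's", which leaves 5% without an SLN on at least one side: 0.05 × 226 = 11.3 patients in stage 1 and 0.05 × 413 = 20.7 over both stages. Under that assumption this is a ceiling on mapping failures with no SLN at all. Section 4.0 expects 90% or more, which would put the ceiling at 10%. Conversions after the search has begun add a number the plan does not state.

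**Step 3: size.** The plan gives no complication rate, sample size or test for this objective, so there is no figure to reproduce. Let
- f = share of searched patients with no SLN removed,
- r1 = event rate in patients with an SLN removed (the rate section 8.0 would report),
- r0 = event rate in searched patients with none removed.

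Rate in all searched patients = (1 − f) × r1 + f × r0. Events outside the report = N × f × r0, with N = 226 (stage 1) or 413 (both stages), taking all as searched. The values of f, r1 and r0/r1 are assumptions.

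| f | r0/r1 | r1 | All searched | Shift (points) | Events outside, N = 226 / 413 |
|---|---|---|---|---|---|
| 1% | 3 | 3% | 0.99×3% + 0.01×9% = 3.06% | +0.06 | 0.20 / 0.37 |
| 5% | 3 | 1% | 0.95×1% + 0.05×3% = 1.10% | +0.10 | 0.34 / 0.62 |
| 5% | 3 | 3% | 0.95×3% + 0.05×9% = 3.30% | +0.30 | 1.02 / 1.86 |
| 5% | 1 | 3% | 3.00% | 0 | 0.34 / 0.62 |
| 5% | 0 | 3% | 0.95×3% = 2.85% | −0.15 | 0 / 0 |
| 10% | 10 | 3% | 0.90×3% + 0.10×30% = 5.70% | +2.70 | 6.78 / 12.39 |

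The sign depends on whether r0 is above or below r1.

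**Step 4: the self-excluding event.** If the only excluded patients are those whose injury forced conversion, r0 is 100% and the ratio far exceeds 10, with f very small. With assumed counts, 4 events in 226 is 1.8%. If one such patient is excluded, the report shows 3/225 = 1.3%; if two, 2/224 = 0.9%. This shows the mechanism. It does not estimate how often it happens.

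**The case against.** The strongest reply is that nothing is lost from the trial. SLN-procedure events are logged without condition, attributed to a phase of surgery, and counted in an all-patient safety evaluation that disregards conversion and mapping. Tables 10.1 to 10.4 separate events before docking, during SLN dissection, during lymphadenectomy and during hysterectomy, so an SLN-phase rate in all patients could be produced from data already planned. This stands. A reader might infer from section 8.0 that such injuries disappear from the trial; the documents do not support that. What remains is that the one SLN-specific safety result the plan defines uses the narrower set.

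Second, few patients would be excluded. One SLN of any type, from either side, is enough. The upper parametrial tissue is also removed separately, examined like an SLN and labelled SLN Parametrium on the specimen lists; if it counts, almost no completed case is excluded. The plan does not say whether it counts, and this route does not reliably cover a conversion before removal.

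Third, the set can be read as patients in whom an SLN step is distinct from the full lymphadenectomy that follows. That is a defensible reading of removal, but it does not cover detection.

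Fourth, many conversions may come before any search. The Table 10.1 examples are disseminated disease and massive adhesions. Leaving those patients out of an SLN denominator is proper, and the fix below does so.

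**Conclusion.** The mismatch is real. The SLN-specific adverse-event rate is conditioned on the search succeeding, while the objective, the log and the conversion rule are not. The rate may be understated. The size is unknown and probably small, because few patients should have no SLN of any type removed; in the assumed range, the shift reaches whole percentage points only with about 10% excluded at tenfold risk. The direction depends on the event rate in the excluded patients.

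Three stronger readings are tempting and not supported:
- A reader might infer that the rate is shown to be biased towards safety, by something like a quarter to a half. The illustrative counts in step 4 give that range only because one or two lost events out of four were assumed; no document gives such counts.
- A reader might infer that the omitted events are the most serious ones. They may include serious ones, but conversion need not follow an SLN injury.
- A reader might take the 95% robotic feasibility in section 2 as capping the excluded share at 5%. That figure measures neither conversion after a search has begun nor failure to find any SLN.

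Severity is minor. The objective is secondary and descriptive, with no test or sample size attached, and the main endpoint in section 11 (sensitivity, with false negative rate and negative predictive value) is unaffected.

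**What to change.** Change the sentence in section 8.0 so that the set for this report is all patients in whom the SLN dissection was started, meaning tracer was injected and SLN exploration begun, whether or not an SLN was removed or surgery was converted. Patients converted before exploration began stay out. Give the rate in patients with at least one SLN removed as a secondary figure, and state whether separately removed parametrial tissue counts as an SLN for that subset.

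The cost is low. Table 10.2 already captures the events, so no new safety form is needed. The start of SLN exploration must be identifiable from the operative record. The reported rate may turn out slightly less favourable.
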